### **Statistical Analysis Plan January 30, 2019**

Survey providers from Internal Medicine (IM) and Family Medicine (FM) to evaluate fall treatment. Educate providers on new protocol. Survey results will be analyzed and used to develop to develop educational care protocol for treatment which will be communicated to providers at grand rounds.

Twelve months after grand rounds, a second survey of IM and FM providers will be conducted to determine how well physical therapy referrals and Vitamin D supplementation dosages aligned with the established protocol.

Associations between pre/post results for categorical variables will be tested with chi-square or Fisher's Exact test.

For comparisons of means for Likert variables, a two sample t-test will be used.

Statistical analysis will be completed using R statistical software program. R Core Team (2019). R: A language and environment for statistical computing. R Foundation for Statistical Computing, Vienna, Austria. URL <https://www.R-project.org/>.

Statistical significance is defined as a p value of 0.05 or less.

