The primary objective of the study is to conduct a retrospective chart review of patients with a diagnosis of falls, and to determine characteristics of the population, specifically, Vitamin D levels, supplementation, and referrals to therapy.

Also to determine if supplementation with Vitamin D increases or decreases risk of falls.

Setting of the Human Research

This study is a combination of retrospective for part 1, survey implementation for part 2, and retrospective again for part 3, and all data will be reviewed and conducted using the electronic health records of The Guthrie Clinic.

Study Design

a. Recruitment Methods:

In part 1 of the study, a retrospective chart review was performed to see how providers handled fallers. A list of patients was selected whose providers had used a variant of the ICD-10 code for fall for their GC visit of FM or IM providers, from the period of January 8, 2016 to November 29, 2017. The patients were stratified according to demographics, BMI, Vitamin D and Ca levels, polypharmacy (defined as more than 4 medications), treatment chosen (supplementation and/or referral to therapy), and cause of fall. The data was then analyzed looking for trends.

In part 2 of the study, an anonymous paper survey was administered to GC providers from IM and FM to evaluate any barriers to Vitamin D supplementation and other treatment options including therapy. Providers who complete the survey will be provided a \$10 gift card for their time involved to complete the survey. A grant application has been approved by the Donald Guthrie Foundation to cover the cost of the gift cards. The survey is administered pre and post education. The post education survey is a shorter version than the pre survey.

In part 3 of the study, new guidelines were established for GC. The IM and FM providers were educated on the new guidelines. After a period of 12 months, another review was performed of patients with ICD-10 codes related to fall to see if referrals and Vitamin D usage had changed.

b. Inclusion and Exclusion Criteria

Patients 65 years and older with a history of falls

c. Study Timelines

See above.

d. Procedures involved in the Human Research

Data will be collected from the electronic medical record. Data will include: Name, Medical Record number, Gender, Age, BMI, Encounter Date, Visit Provider, Visit Location; Diagnosis code related to falls and encounter diagnosis name.

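### The SAP draws its 12-month practice conclusion from a provider survey and assigns no analysis to the chart reviews the protocol plans for the closely related question

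*SAP*

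**What the plan says.** The SAP describes two provider surveys. The first (first paragraph) is to evaluate how falls are treated, and its results feed the care protocol presented at grand rounds. The second paragraph states that, twelve months later, "a second survey of IM and FM providers will be conducted to determine how well physical therapy referrals and Vitamin D supplementation dosages aligned" with that protocol. The tests that follow are chi-square or Fisher exact for categorical pre/post results and a two-sample t-test for Likert items.

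The protocol is built differently. Its Setting section says: "This study is a combination of retrospective for part 1, survey implementation for part 2, and retrospective again for part 3". Under Study Design, Recruitment Methods:

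- Part 1: "a retrospective chart review was performed to see how providers handled fallers", using visits "from the period of January 8, 2016 to November 29, 2017".
- Part 2: the provider survey is given "to evaluate any barriers to Vitamin D supplementation and other treatment options including therapy", and "The survey is administered pre and post education". No 12-month interval is attached to it.
- Part 3: twelve months after providers were educated, "another review was performed of patients with ICD-10 codes related to fall to see if referrals and Vitamin D usage had changed".

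The Objectives section adds: "The primary objective of the study is to conduct a retrospective chart review of patients with a diagnosis of falls". The survey-risks statement describes the survey as anonymous and optional.

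**The concern.** Whether providers changed what they do for older patients who fall is the stated purpose of Part 3, and the protocol reads the answer from the medical record. The SAP reads its practice conclusion from what providers say they do. These are different endpoints. One is recorded care with the patient as unit. The other is self-report with the provider as unit, from those who chose to answer, and anonymity prevents linking any answer to a patient.

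An analyst following the SAP would produce a practice conclusion from the survey and would have no specified analysis for the Part 1 or Part 3 charts, including those that serve the primary objective. Neither document says which source governs. That leaves the choice of source, unit and cohort to be made after the data are in hand.

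**Working it through.** No arithmetic applies. The documents state no sample size, rate or effect size, so the check sets the texts side by side.

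| Item | Protocol | SAP |
|---|---|---|
| Source of 12-month information on practice | Second review of fall-coded patients (Part 3) | Second provider survey |
| Question | Did referrals and Vitamin D usage change? | Did referrals and dosages align with the care protocol? |
| Unit | Patient | Provider |
| Purpose of the survey | Barriers to treatment | Fall treatment (first survey); alignment (second survey) |
| Chart analysis | Part 1 data examined for trends, nothing more specific | None assigned |

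1. *Are the questions the same?* Not quite. Change needs a before and an after; alignment needs a standard and an after. Both depend on what was done about referral and Vitamin D at follow-up, so they are closely related.
2. *Is Part 3 really chart-based?* Yes. It selects patients by ICD-10 code, and the Setting section calls it retrospective and places the data in the electronic health records.
3. *Does one document supersede the other?* No. Both are dated January 30, 2019, and neither states an order of precedence.
4. *Does the SAP mention charts anywhere?* No. The word survey appears three times; chart, record, patient, retrospective and ICD do not appear.
5. *Could the categorical-test sentence cover charts?* It names no data source, so it could be applied to chart proportions. But it follows two paragraphs that describe only surveys, and it gives no cohort, time window or unit. It does not assign the test to chart data.
6. *Is there a chart baseline to use?* Yes. Part 1 lists Vitamin D level and treatment chosen (supplementation, referral or both). Dose is not among the variables Part 1 names, so a chart-based statement about dosages depends on dose being recorded in the Part 3 charts.
7. *Can the error be sized?* No. That would need the number of charts, the number of survey respondents, the referral and supplementation rates, and the agreement between self-report and record. None is given.

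**The case against.** The best defence is that the SAP is silent on charts and does not reject them. Its pre/post sentence is general enough to fit chart proportions, and an analyst would have the protocol of the same date to hand. A post-education survey is part of the protocol, so a second survey contradicts nothing. Evaluating barriers to treatment and evaluating fall treatment overlap. An alignment question needs no baseline, and the SAP never proposes to compare survey answers with the Part 1 charts. Twelve-month change is not a listed objective.

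Most of this is right, and it limits the point. A reader might infer that the SAP has replaced or dropped the chart review; the text does not support that, because nothing in it cancels Part 3. A reader might also take the second survey itself as the conflict; it is not. The conflict is the use made of it.

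The defence does not supply an analysis. Change is the stated purpose of Part 3, a chart review is the primary objective, and the SAP assigns a test to neither. Allowing that the categorical test could be borrowed for the charts is not the same as planning it.

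**Conclusion.** The point holds as an unreconciled difference in data source together with an omission. The SAP answers a practice question from provider self-report, while the protocol plans chart data for the closely related question, and the SAP assigns no analysis to those charts. This rests on the wording alone and needs no numerical assumption.

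No magnitude is claimed. A reader might want to attach a non-response range to the survey, or an inflated type I error to a chart comparison that counts repeat visits. Neither is supported. Every response rate, visit count or correlation would have to be assumed, the first would apply to any optional survey, and the second is a separate issue: Part 1 describes a list of patients, and nothing says visits would be treated as independent.

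The change should be made before the data are analysed, because it decides which data carry the practice conclusion and gives the primary objective an analysis.

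**What to change.** Reconcile the SAP's second paragraph with protocol Parts 2 and 3, and add to the SAP text along these lines:

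> Change in practice will be assessed from the Part 1 and Part 3 charts of patients aged 65 years and older with a fall-related ICD-10 code. Each patient counts once per period. The proportion with a therapy referral and the proportion with Vitamin D supplementation will each be compared, Part 3 versus Part 1, as a difference with 95% CI and a chi-square or Fisher exact test. A sensitivity analysis will exclude patients who appear in both periods. Alignment with the established protocol will be reported from Part 3 charts where dose is recorded, using criteria fixed before the data are analysed. Vitamin D levels, supplementation and referrals will be summarised descriptively for the primary objective. The second provider survey will be reported separately and its results labelled provider-reported.

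The alignment criteria are tied to analysis and not to abstraction because the protocol describes the Part 3 review in the past tense, so abstraction may already have been done.

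The cost is SAP wording and modest extra abstraction of recorded dose, with no new recruitment. Repeat encounters go unused, and the sensitivity analysis loses the patients seen in both periods. Part 1 charts need re-abstraction only if dosage is to be compared before and after.

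Two additions are optional. Part 1 covers 692 days (359 in 2016 plus 333 in 2017), so if Part 3 covers 12 months, a check restricted to the last 365 days of Part 1 would match the windows. The data list in Study Design, section d, could be brought into line with the variables Part 1 names, although it is not stated to be exhaustive.

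This text does not supply an analysis for the separate objective on supplementation and falls risk, nor does it allow for clustering of patients by provider.

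### The SAP asks how well practice aligned with the protocol but commits to no estimate of alignment and no confidence interval, only to pre/post tests read against 0.05

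*SAP*

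**What the plan says.** The SAP is one page without numbered sections. Its second paragraph gives the purpose of the survey held twelve months after grand rounds: "to determine how well physical therapy referrals and Vitamin D supplementation dosages aligned with the established protocol". Three analysis statements follow:

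- Categorical items: "Associations between pre/post results for categorical variables will be tested with chi-square" or Fisher's exact test.
- Likert items: "For comparisons of means for Likert variables, a two sample t-test will be used".
- Decision rule: "Statistical significance is defined as a p value of 0.05 or less".

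The Protocol (Study Design, Recruitment Methods) describes the survey in part 2: "an anonymous paper survey was administered to GC providers from IM and FM", and "The survey is administered pre and post education". For the twelve-month follow-up, however, part 3 describes a chart review: "another review was performed of patients with ICD-10 codes related to fall to see if referrals and Vitamin D usage had changed".

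Neither document states a number of providers or patients, an expected gain, a target level of alignment, a definition of alignment for any item, or a confidence interval.

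**The concern.** Asking how well practice aligned is mainly a question about a level: after education, what share of answers or records agrees with the protocol, and how precisely is that share known? A test of association between wave and answer addresses a different question, namely whether the two waves differ by more than chance would explain. A significant result does not show that alignment is good, because it may have risen from very low to low. A non-significant result does not show that nothing improved, because the data may have been too few to tell.

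What is at stake is the message that the departments take from the education programme. With a p value as the only committed output, readers could not tell a programme that left most practice out of line from one that brought nearly all of it into line. They also could not tell an informative null result from an uninformative one.

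**Working it through.** The plan contains no power calculation, rate or sample size, so there is no figure of its own to reproduce. Every n and rate below is an assumption used for illustration. The tests are taken as two-sided at 0.05 (the SAP does not state sidedness). The waves are treated as independent, because the survey is anonymous and no linkage of forms is described.

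**Step 1. Does the planned output give the level?** Take 30 forms per wave and two possible results.

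| Aligned before | Aligned after | Fisher p | Post-education level (Wilson 95% CI) |
|---|---|---|---|
| 3/30 | 9/30 | 0.104 | 30% (17% to 48%) |
| 20/30 | 26/30 | 0.125 | 87% (70% to 95%) |

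The gain is 6/30 = 20 points in both rows and the p values nearly agree, yet the answers to the SAP's question are far apart. This does not depend on sample size: a test of change does not report a level at any n.

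**Step 2. What would estimates add?** Take 20/40 aligned before and 27/40 after.

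- Chi-square without correction: pooled proportion = 47/80 = 0.5875. X² = 0.175² / (0.5875 × 0.4125 × 2/40) = 0.030625 / 0.012117 = 2.53, so p = 0.11. With continuity correction, or by Fisher, p = 0.17.
- Wilson interval for the post level: [p + z²/2n ± z√(p(1−p)/n + z²/4n²)] / (1 + z²/n), with p = 0.675, n = 40, z = 1.96. The centre is (0.675 + 0.0480)/1.0960 = 0.660 and the half-width is (1.96/1.0960) × √(0.005484 + 0.000600) = 0.139. Result: 67.5%, 95% CI 52% to 80%.
- The Wilson interval for 20/40 by the same formula is 0.352 to 0.648.
- Newcombe interval for the difference of 0.175: lower limit = 0.175 − √(0.155² + 0.148²) = −0.039; upper limit = 0.175 + √(0.124² + 0.148²) = 0.368. Result: +17.5 points, 95% CI −4 to +37.

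Under the SAP's rule the result is simply not significant. The estimates show about two thirds aligned, and a change that could be anything from a slight loss to a large gain.

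**Step 3. How often would a real gain give p above 0.05?** For each pair of counts (i, j), multiply the two binomial probabilities and sum over the pairs with p of 0.05 or less. That sum is the power, and the miss rate is 1 − power. For a true rise from 50% to 70%:

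| Forms per wave | Fisher power | Fisher miss rate | Uncorrected chi-square power |
|---|---|---|---|
| 40 | 37% | 63% | 46% |
| 60 | 54% | 46% | 62% |
| 100 | 79% | 21% | 83% |
| 150 (normal approximation) | – | – | about 95% |

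The size of the gain matters as much as n:

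- True rise from 50% to 80% at 40 per wave: Fisher power is 75%, a miss rate of 25%.
- True rise from 40% to 50%: Fisher misses it 74% of the time at 100 per wave. By normal approximation the miss rate is still about 48% at 200.
- Likert items, true difference of half a standard deviation: t-test power is 49% at 30 per wave and 94% at 100.

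**The case against.** The strongest reply has three parts.

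**The estimates are implicit.** A comparison of means requires means, a chi-square table contains both sets of counts, and R prints a confidence interval by default for its t-test and, as an odds ratio, for a 2×2 Fisher test. This is fair as far as it goes: the gap is in what the plan commits to report, and the tests are not wrong. But default output is not a planned analysis, R's chi-square test prints no interval, and an odds ratio is not a level of alignment.

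**A pre/post test does address part of the aim.** The Protocol's part 3 asks whether referrals and Vitamin D usage changed, and a test of pre/post difference bears on that. This stands. A reader might infer that the plan leaves its question wholly unanswered; the documents do not support that. What goes unaddressed is the level, and the size and precision of the change.

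**The loss of power is assumed.** A reader might infer that the 0.05 rule will often turn a real gain into a null result. The documents do not support that either, because they give no sample size and no expected gain. The follow-up data may also come from the part 3 chart review, where the unit is the patient. The part 1 review ran from January 2016 to November 2017, so the counts could be much larger than a provider survey would yield, although none is given. Nor does the SAP say that p above 0.05 will be read as no change. That risk arises because no other way of reading the result is offered.

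**Conclusion.** The point holds in a limited form. The SAP poses a question about how well practice aligned and commits only to significance tests. The mismatch can be read directly from the SAP and rests on no assumed number: the planned analysis does not state the level of alignment, the size of the change or the precision of either.

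The risk of misreading a real gain is conditional. It is substantial if the data are a small provider survey or the gain is modest, and minor for a 20-point gain with about 150 or more per period. The figures assume independent answers and two-sided tests. Because the sample size is unknown, intervals are all the more useful: they let a reader judge whether a null result is informative.

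This should be changed, but it does not invalidate the tests already named.

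**What to change.** Amend the SAP as follows:

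1. Define, for each item on referral and on Vitamin D supplementation, what counts as aligned, by reference to the established protocol. Without this the proportion cannot be computed.
2. State whether alignment is measured from the second survey (SAP) or from the part 3 chart review (Protocol), and reconcile the two documents. This fixes the unit of analysis and the n.
3. Make the main results the post-education proportion aligned with a Wilson 95% confidence interval, and the pre/post difference in proportions (or in Likert means) with a 95% confidence interval.
4. Keep the chi-square, Fisher and t-test p values as secondary.
5. State that p above 0.05 is not in itself read as no change, and that the interval is what shows which changes remain compatible with the data.

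The cost is a few lines of wording and standard R output, with no new data. The drawback is that the intervals may be visibly wide; at 40 per wave, the example interval for the difference spans about 41 points (−4 to +37).
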